7.8. EARLY TERMINATION VISIT

In the event of an early subject termination, the clinical site should, at a minimum, document Adverse Events and Concomitant Medications changes. The clinical site will additionally complete the Study Exit eCRF. Refer to **Section 7.7** Schedule of Events.

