To date, all follow up visits through 18 months have been completed; 15 out of 30 subjects completed 18 months of follow up. Three subjects have had other nasal surgery procedures and consequently exited the study; two subjects after the 12 month visit and one subject after the 18 month visit.

		Score	Change from baseline			Change from baseline % Change from baseline			Change from baseline	
Visit	N	Mean (SD)	Mean (SD)	LS Mean (95% CI)	p-value	Mean (SD)	LS Mean (95% Cl)	p- value		
1 Week	30	24.2 (16.14)	-52.5 (22.77)	-52.7 (-58.83, -46.55)	<.001	-67.2 (21.34)	-67.2 (-74.98, -59.51)	<.001		
1 Month	30	27.0 (23.95)	-49.7 (25.56)	-49.9 (-58.79, -40.93)	<.001	-64.8 (29.09)	-64.9 (-75.92, -53.86)	<.001		
3 Months	29	28.4 (26.90)	-48.4 (27.84)	-47.9 (-57.85, -37.96)	<.001	-63.4 (34.45)	-62.7 (-75.70, -49.66)	<.001		
6 Months	30	33.3 (29.69)	-43.3 (31.28)	-43.5 (-54.61, -32.44)	<.001	-56.2 (37.85)	-56.3 (-70.46, -42.07)	<.001		
12 Months	29	35.2 (29.17)	-40.9 (31.23)	-39.7 (-51.22, -28.11)	<.001	-53.1 (40.64)	-51.6 (-67.07, -36.12)	<.001		
18 Months	15	38.0 (33.32)	-41.7 (36.24)	-40.7 (-55.01, -26.30)	<.001	-51.3 (41.76)	-52.2 (-70.59, -33.87)	<.001		

A longitudinal summary of NOSE score is provided in the table below and these results demonstrate significant improvements over baseline for all time points measured.

This first in man study demonstrated the safety and effectiveness of the absorbable Implant to provide lateral cartilage support in patients with NVC as primary contributor to NAO.

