10.2. STATISTICAL HYPOTHESES

Primary Efficacy Endpoint:

• The primary efficacy endpoint is the proportion of treatment responders at 6 months post procedure. Since there is no direct comparison group in this study, the primary efficacy hypothesis is a superiority comparison to a target proportion:

Null Hypothesis H₀: the proportion of responders at 6 months is = 0.50, versus Alternative Hypothesis H_A: the proportion of responders at 6 months is \neq 0.50

• There are no other formal statistical hypotheses.

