10.5. SAMPLE SIZE

The primary study hypothesis is a superiority comparison to a target proportion:

Null Hypothesis H₀: the proportion of responders at 6 months is =0.50, versus Alternative Hypothesis H_A: the proportion of responders at 6 months is \neq 0.50

See section 10.4.2 for the definition of response. This hypothesis will be evaluated using an exact test.

In order to have > 90% power to rule out a response rate \leq 50% at a 5% (2-sided) significance level, assuming a true response rate of 66%, 150 subjects with 6 month follow-up are needed. Assuming about 10% drop-out rate, up to 170 subjects will be enrolled. All mITT subjects will be used for this comparison, regardless of protocol deviations.

The assumed response rate is the minimum value expected to be consistent with previous trials, where an 80% response rate at 6 months was observed.

Sample size calculations were performed using the package RCTDesign for R version 3.2.3.

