#### SUPPORTIVE AND SENSITIVITY ANALYSES 4.2.2.1.

The primary endpoint analysis will be repeated using the PP analysis set. In order to quantify the impact of missing data on the primary analysis results, missing data may be imputed using 2 techniques:

- Last observation carried forward (LOCF) 1.
- Subjects with missing data classified as non-responders 2.

Since the efficacy of the device may deteriorate over time, LOCF represents the least conservative imputation technique, while classifying subjects with missing data as nonresponders represents the most conservative technique. These two analyses are reasonable upper and lower bounds for the response result, accounting for the missing data.

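### No NOSE score or breathing VAS is required when a subject leaves early, so the missing-data analyses rest on an early post-operative score or an assumption

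*Protocol*

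**What the plan says.** Three places in the protocol govern early exit. Section 7.8 says that "the clinical site should, at a minimum, document Adverse Events and Concomitant Medications changes", and adds the exit form. Section 5.4 repeats adverse events, medication changes and the exit form, and adds whatever data are available. The Early Exit column of the schedule (7.7) marks only the adverse event assessment and the exit form. Section 7.2.1 lists NOSE, and 7.2.2 lists the VAS, at named visits only, and exit is not among them.

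On analysis, SAP 4.2.2 restricts the primary test to the 6-month evaluable (6ME) set, meaning subjects with a 6-month NOSE score taken in clinic or by telephone. Protocol 10.4.2 and SAP 4.2.2.1 name two possible analyses for missing data: last observation carried forward (LOCF), and missing counted as non-response. Both documents word these as things that may be done. The SAP explains: "Since the efficacy of the device may deteriorate over time, LOCF represents the least conservative imputation technique". It treats the two results as reasonable upper and lower bounds.

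On who leaves, Protocol 2.2 reports of the earlier study: "Three subjects have had other nasal surgery procedures and consequently exited the study". The same sentence places two of those exits after the 12-month visit and one after the 18-month visit.

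**The concern.** The score at the time a subject withdraws is the most recent evidence on whether the treatment was working for that person. If leavers tend to be doing poorly, that score matters most and is the one the schedule does not ask for. Consider a subject who feels well at month 1, relapses and withdraws in month 4. The primary analysis omits this subject. LOCF carries a 1- or 3-month score to month 6. Only the analysis that counts missing as failure registers the relapse, and it does so by assumption.

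The same gap affects the responder and VAS endpoints at 12, 18 and 24 months, where the prior study does show exits for further nasal surgery.

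**Working it through.** **Inputs.** The null is that "the proportion of responders at 6 months is = 0.50" (Protocol 10.2), tested "at a 5% (2-sided) significance level" (10.5). The design aim begins "In order to have > 90% power to rule out a response rate" of 50% or less. The protocol then states: "assuming a true response rate of 66%, 150 subjects with 6 month follow-up are needed". It continues: "Assuming about 10% drop-out rate, up to 170 subjects will be enrolled". SAP section Sample Size Justification instead gives 120 evaluable, 20% drop-out, and 150 to 170 enrolled.

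**Reproducing the plan's figures.** Reject upwards at the smallest count whose upper binomial tail under 0.50 is at most 0.025.

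- N = 150: reject at 88 or more; power at 66% is 97.5%.
- N = 120: reject at 72 or more; power is 93.0%.
- Enrolment: 150/0.9 = 167, against 170 stated; 120/0.8 = 150, as stated.

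Both power claims hold.

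**Range between the two sensitivity analyses.** Let m be the number missing, k = N − m the number scored, and x the responders among those scored. Missing as failure gives x/N. LOCF with every carried score a response gives (x + m)/N, which is an upper extreme. P-values are exact two-sided binomial tests against 0.50.

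| Case | Scored | Missing = failure | LOCF upper extreme |
|---|---|---|---|
| SAP: N = 150, m = 30, 66% | 79/120 = 65.8% (p = 0.0007) | 79/150 = 52.7% (p = 0.57) | 109/150 = 72.7% (p < 0.001) |
| Protocol: N = 170, m = 20, 66% | 99/150 = 66.0% (p = 0.0001) | 99/170 = 58.2% (p = 0.038) | 119/170 = 70.0% (p < 0.001) |
| SAP: N = 150, m = 30, 80% | 96/120 = 80.0% | 96/150 = 64.0% (p = 0.0008) | 126/150 = 84.0% |
| Protocol: N = 170, m = 20, 80% | 120/150 = 80.0% | 120/170 = 70.6% (p < 0.001) | 140/170 = 82.4% |

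In the SAP case at 66%, the two bounds disagree on whether the null is rejected. Missing as failure would need 88/120 = 73.3% among those scored. In the protocol case at 66%, 99 of 170 is exactly the rejection boundary.

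**Would early scores lean favourable?** Protocol 2.2 gives prior-study mean NOSE of 27.0 at 1 month, 28.4 at 3 and 33.3 at 6, from an implied baseline of 24.2 + 52.5 = 76.7. A rough normal approximation to the chance of a 20% or greater reduction is Φ((−20 − mean % change)/SD):

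- 1 month: (−20 + 64.8)/29.09 = 1.54, giving 94%.
- 3 months: (−20 + 63.4)/34.45 = 1.26, giving 90%.
- 6 months: (−20 + 56.2)/37.85 = 0.96, giving 83%.

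Early scores are thus about 7 to 11 points more favourable than 6-month scores. Adding that difference to 66% gives a carried-forward response of about 73% to 77%. LOCF then gives (79 + 30 × 0.73 to 0.77)/150, about 101 to 102 of 150, or 67% to 68%. In the protocol case it gives (99 + 20 × 0.73 to 0.77)/170, about 114 of 170, or 67%. These are more moderate upper values than 72.7% and 70.0%.

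**The case against.** Four points deserve weight.

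1. **A reader might infer that failures are the ones who leave.** The documents do not show this for month 6. All three reported exits came after the 12- or 18-month visit, and all 30 prior-study subjects had a 6-month score. Further nasal surgery is suggestive, but it is not described as treatment failure. For the primary endpoint the premise is a plausible risk only. For the 12- to 24-month endpoints the evidence is direct, though thin.

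2. **A reader might infer that the plan must carry scores forward or assume failure, or that the relapsing subject is hidden.** Neither follows. Both imputations are optional and neither is the primary analysis. Counting missing as failure does register that subject, and the SAP openly calls LOCF the less conservative bound. What stands is that the bracket is wider than it need be.

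3. **A reader might infer that an exit score is ruled out.** It is not. The wording of 7.8 sets a floor, 5.4 takes in available data, and a 6-month NOSE may be taken by telephone. But a site that follows the schedule as printed will not ask for either form.

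4. **The remedy is partial.** Under Protocol 7.3, subjects lost to follow-up are those who could not be reached by calls and a certified letter, so they give no exit score. The documents do not split drop-out into withdrawals and losses. An exit score taken before the 6-month window is still carried forward. All of this stands and limits the gain.

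**Conclusion.** The gap is real. No section requires NOSE or the breathing VAS at early exit, so a plan followed as written takes no outcome score from a subject who withdraws while still in contact with the site. This is a cheap improvement in data collection. It does not show that the primary result will be biased.

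Its size depends on assumptions. At the 66% planning rate and the SAP's 20% drop-out, the two optional analyses span 20 points and straddle the rejection boundary. In the protocol case the span is about 12 points and both ends reject. Both upper ends assume that every carried score is a response, and the more moderate estimate is about 67% to 68%. At 80%, the response rate that both documents cite from earlier experience, every scenario rejects 0.50. The gap therefore matters most if response is near the planning rate and drop-out is near the SAP's figure, and for durability beyond 12 months.

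**What to change.** - **Protocol 7.7:** mark the NOSE scale and the NAO Breathing Assessment under Early Exit.
- **Protocol 5.4 and 7.8:** ask for both forms at exit, in clinic or by telephone. Where the subject leaves for another nasal procedure, ask for them before that procedure where possible. This concerns only when the forms are completed, not the procedure itself.
- **SAP 4.2.2.1:** use the exit NOSE as the last observation, and as the 6-month score if it falls in the 6-month window.
- **SAP 2.1 and 4.4.2:** allow exit scores to be assigned to the visit window they fall in, so that exit VAS values can enter the repeated-measures model. Section 2.1 appears to limit analysis to planned visits (its last sentence is cut off in the copy reviewed), so it needs an explicit allowance.
- **Reconcile 7.7 with 7.8:** the text asks for concomitant medication changes at early exit, but the column has no mark for them.

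Cost: a protocol amendment to one table column and two short sections, and a few SAP sentences. Both forms already exist and take a few minutes per exiting subject. Some subjects will decline, those lost to follow-up will have no exit score, and earlier exit scores will still be carried forward.

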8. ASSESSMENT OF SAFETY

8.1. SPECIFICATION OF SAFETY PARAMETERS

All Serious Adverse Events (SAE), Adverse Device Effect (ADE) and Serious Adverse Device Effects (SADE) will be collected and documented through the end of subject participation in the study. In addition, all non-serious device and procedure-related Adverse Events (AE) and all non-serious head and neck, and/or respiratory related AEs will also be collected and documented.

The primary safety endpoint evaluation will consider nasal procedure related and Latera related adverse events through 6 months post-procedure.

The following information for each AE, ADE, SAE and SADE will be collected:

- Date of onset
- Status and/or Outcome
- Date of resolution
- Adverse Event/Effect type
- SAE or SADE
- Severity of event
- Relation to Study Device and/or procedure
- Action taken
- Descriptive narration of Event/Effect

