8.1.1. DEFINITION OF ADVERSE EVENTS (AE) AND SERIOUS ADVERSE EVENTS (SAE)

An adverse event (AE) or effect is defined as any untoward and unintended medical occurrence experienced by a clinical study subject. An AE can therefore be any unfavorable and unintended sign, symptom, or disease temporally associated with the use of the investigational product, whether or not related to the product.

The following events will be considered to be serious adverse events (SAE) and must immediately and without delay (within 24 hours) be reported to the study Sponsor by fax and/or email. These events must be reported whether or not the Investigator believes they are related to study procedures, activities or device:

- Death (the investigator will provide a copy of any post-mortem findings, including histopathology reports if available).
- Life-threatening event or injury
- Disability significant, persistent, or permanent change, impairment, or damage or disruption in the subject's body function/structure, physical activities or quality of life

Version 2.0 tember 7, 2017

- Necessitate immediate medical or surgical intervention to:
 - Preclude permanent impairment of a body function or permanent damage to a body structure; or
 - Relieve unanticipated temporary impairment or damage.
- Prolongation of a hospitalization
- New hospitalization

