8.3. TIME PERIOD AND FREQUENCY FOR EVENT ASSESSMENT AND FOLLOW-UP

The occurrence of an AE or SAE may come to the attention of study personnel during study visits and interviews of a subject presenting for medical care, or upon review by a study monitor.

All device or procedure-related AEs, including local and systemic reactions not meeting the criteria for SAEs, will be captured on the appropriate CRF. Information to be collected includes event description, time of onset, clinician's assessment of severity, relationship to study product (assessed only by those with the training and authority to make a diagnosis) or concomitant procedures, and time of resolution/stabilization of the event. All AEs occurring while on study must be documented appropriately regardless of relationship. All AEs will be followed to adequate resolution.

Any medical condition that is present at the time of the participant's procedure will be considered as a baseline condition or comorbidity, and will not reported as an AE. However, if the subject's condition deteriorates at any time during the study, and the condition is procedure/device related, it will be recorded as an AE. AEs will be recorded in the data collection system throughout the study.

Changes in the severity of an AE will be documented. AEs characterized as intermittent require documentation of onset and duration of each episode.

At each study visit, the investigator will inquire about the occurrence of AE/SAEs since the last visit. Events will be followed for outcome information until resolution or stabilization.

8.4. **REPORTING PROCEDURES**

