8.4.1. ADVERSE EVENT REPORTING

The investigator must document all AEs on the AE Source Documents and subsequently enter this information into the electronic case report form, which will be reviewed by the study monitor and provided to the study sponsor. AE source documentation must be signed off by the procedure-trained investigator.

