10.4.4. SAFETY ANALYSES

Two analysis sets will be used to *summarize* adverse events. The ITT analysis set will be used to summarize acute adverse events (through 1 month post procedure), and the mITT analysis set will be used to summarize adverse events over the entire duration of follow-up. The primary safety reporting time-point is 6 months post-implant.

The overall incidence (i.e., number and percent of subjects with 1 or more adverse event in each class) of adverse events, serious adverse device events, serious adverse events, fatal adverse events, and device related events (e.g., possibly, probably or definitely related) will be calculated for the acute phase, through 6 months post-procedure and for the entire duration of follow-up. The overall incidence of mild, moderate and severe events will be calculated by considering the most severe event for each subject.

In addition, the overall incidence for each adverse event type will be calculated. The adverse event types will be classified according to the following categories:

- Excessive Inflammation
- Significant Foreign body sensation
- Excessive Pain or discomfort
- Infection
- Implant Extrusion, defined as body rejection of implants
- Implant Retrievals, defined as surgeon or subject initiated removal of implants not associated with body rejection of implant
- Implant bent or fractured
- Implant loose
- Implant migration
- Skin irritation
- Hematoma
- Unintended perforation of the skin
- Other

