#### 5.1. ADVERSE EVENTS

Adverse events (AEs) will be coded. Adverse events through 7 days post procedure will be summarized for the ITT analysis set, and cumulative summaries will be produced for the mITT analysis set.

Categories of adverse events include:

- Device-related AEs
- Implant procedure-related AEs
- Serious AEs
- Adverse Device Effect (ADE)
- Device retrievals
- Moderate or Severe AEs

Summaries may also be produced by follow-up interval.

For each AE category, the percentage of subjects who experienced at least one occurrence of the given event will be calculated. Overall frequency by coded type will also be summarized. In addition, each AE will be listed for each subject. These listings will include onset interval, relationship to procedure and implant, severity, whether the event is an ADE, SADE or SAE, onset and resolution dates, action taken and outcome.

If the timing of events such as implant retrieval is of interest, this will be analyzed using Kaplan-Meier techniques.

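### The protocol gives two collection scopes for non-serious unrelated adverse events, so the overall, severity and by-type AE rates have no single defined event scope

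*Protocol*

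**What the plan says.** Protocol 8.1 sets out what is collected. SAEs, ADEs and SADEs "will be collected and documented through the end of subject participation in the study". For the rest it adds that "all non-serious device and procedure-related Adverse Events (AE) and all non-serious head and neck, and/or respiratory related AEs will also be collected and documented". Non-serious events that are unrelated and lie outside those body systems are not mentioned.

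Other parts of section 8 are wider:

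- 8.1.1 defines an AE as "any untoward and unintended medical occurrence experienced by a clinical study subject", with no body-system limit.
- 8.2.2 says that the assessed relationship does not decide what is reported, and asks for doubtful observations to be reported.
- 8.3 says that "All AEs occurring while on study must be documented appropriately regardless of relationship". The same section also has a narrower sentence: "All device or procedure-related AEs, including local and systemic reactions not meeting the criteria for SAEs, will be captured on the appropriate CRF".
- 8.4.1 says that "The investigator must document all AEs on the AE Source Documents and subsequently enter this information into the electronic case report form".

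Protocol 7.1.4 and the schedule of events add a time limit: after the 12-month visit only adverse device effects are collected.

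On the analysis side, Protocol 10.4.4 reports "The overall incidence (i.e., number and percent of subjects with 1 or more adverse event in each class) of adverse events" and the incidence of mild, moderate and severe events by each subject's worst event. SAP 5.1 has a category "Moderate or Severe AEs" and an overall frequency by coded type. None of these rows is limited by relationship or body system.

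**The concern.** The two rules disagree on one class of event: non-serious, judged unrelated, and outside the head, neck and airway. A site working from 8.1 has no instruction to collect it. A site working from 8.4.1 must enter it in the eCRF. The unrestricted rows count whatever was entered, so what they measure depends on which section was followed. With about 25 sites planned, one table may mix two definitions of a countable event, and nothing in the table would show it.

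At stake is the meaning of the overall, severity-graded and by-type AE rates, and whether they can be compared between sites or with other studies. Appendix II says that the data are meant to support possible regulatory applications and publications, where a rate needs a stated event definition.

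**Working it through.** No stated figure can be reproduced, because the documents give no expected overall or moderate/severe AE rate. The check compares the collection rules with the rows that use them.

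**Step 1: collection rules by type of event**

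| Type of event | 8.1 | 8.3 and 8.4.1 | 7.1.4, after 12 months |
|---|---|---|---|
| Serious (SAE) | yes | yes | only if a device effect |
| ADE, SADE | yes | yes | yes |
| Non-serious, device- or procedure-related | yes | yes | only if a device effect |
| Non-serious, unrelated, head and neck or respiratory | yes | yes | no |
| Non-serious, unrelated, elsewhere | not listed | yes | no |

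Up to 12 months, the two rules differ only in the last line. After 12 months, 7.1.4 departs from both. The 8.1 scope is therefore common ground through 12 months and not beyond.

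**Step 2: which rows depend on the last line**

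- Primary safety endpoint (nasal-procedure- and Latera-related AEs through 6 months): no. Change 0.
- Device-related, procedure-related, ADE, SADE and SAE summaries through 12 months: no.
- Overall AE incidence and worst-severity incidence (10.4.4): yes.
- Moderate-or-severe category and frequency by coded type (SAP 5.1): yes.

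**Step 3: illustration of size, all inputs assumed**

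Let p be the share of subjects with an AE in the 8.1 scope. Let q be the share with a non-serious, unrelated AE outside it, taken as independent of p. Let f be the share of subjects at sites that follow 8.3 and 8.4.1.

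Reported incidence = p + f × (1 − p) × q

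With p = 20%:

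- All sites on 8.1 (f = 0): 20%, whatever q is.
- All sites on 8.3/8.4.1 (f = 1):
  - q = 5%: 0.20 + 0.80 × 0.05 = 24%
  - q = 15%: 0.20 + 0.80 × 0.15 = 32%
  - q = 30%: 0.20 + 0.80 × 0.30 = 44%
- Half the subjects under each rule (f = 0.5), q = 15%: 0.20 + 0.5 × 0.80 × 0.15 = 26%, which is neither the 20% of one rule nor the 32% of the other.

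For p from 10 to 30% and q from 5 to 30%, the gap between the rules is (1 − p) × q. The smallest is 0.70 × 0.05 = 3.5 points and the largest is 0.90 × 0.30 = 27 points.

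The nearest figures in the documents do not fix p or q. The earlier German study had device-related events in 4 of 30 subjects (13.3%), and Protocol 2.3.2 gives complication rates for the concomitant procedures. Both concern related events, which both rules collect.

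**The case against.** The best case for the plan is that 8.1 is worded as an addition and never says only, whereas 7.1.4 does say so when it restricts collection after 12 months. Read with 8.2.2, 8.3 and 8.4.1, the protocol may simply intend all AEs. The sponsor supplies the source documents, uses one EDC system and monitors every site, so practice could be uniform. The affected rows are descriptive, in a single-arm study with no formal safety hypothesis. The named AE types in 10.4.4 are nearly all local or implant events, so unrelated systemic events would mostly fall under Other.

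Much of this stands as a limit on reach. It does not remove the conflict: naming particular body systems in 8.1 has no purpose if every AE is collected anyway. The opposite reading, that all AEs in 8.3 and 8.4.1 means all within 8.1, is not stated and sits badly with the definition in 8.1.1. The narrower CRF sentence in 8.3 adds to the doubt.

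A reader might infer more than the documents support:

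- **That the main safety result is compromised.** It is not, since both rules collect related events in full.
- **That sites will in fact diverge.** They may, but nothing shows that they do.
- **That unrelated events never reach the Medical Monitor.** Protocol 10.4.7.1 says that this role reviews all AEs, and 8.2.2 favours reporting. An event left out under 8.1 could be missed, but that is a worst case.
- **That post-anaesthetic symptoms would be lost.** An anaesthetic effect is a listed septoplasty risk, so in subjects having septoplasty it would plausibly count as procedure-related and fall inside 8.1.

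**Conclusion.** The conflict is real and lies in the current text. Because 8.1 and 8.3/8.4.1 set different scopes and no section takes precedence, four sets of descriptive rows have no single event definition: overall incidence and worst-severity incidence in Protocol 10.4.4, and moderate or severe AEs and frequency by coded type in SAP 5.1. They may pool different definitions across sites.

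The primary safety endpoint and the device-related, procedure-related, ADE, SADE and SAE summaries through 12 months stand as planned. The size cannot be found from the documents. The 3.5 to 27 points rest wholly on assumed p and q and on their independence, and show only that the choice of rule could matter. This should be corrected before database lock, but it does not threaten the study's main safety conclusion.

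**What to change.** **Protocol.** Reconcile 7.1.4, 8.1, 8.3 and 8.4.1 to one collection scope in the same words, and state what is collected after 12 months.

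**Protocol 10.4.4 and SAP 5.1.** Through 12 months, compute the overall, severity and by-type AE rows on events in the 8.1 scope: serious, device- or procedure-related, head and neck, respiratory. Both rules require these, so the rows stay valid for data already collected under either. Label each row with that scope and list any other collected events separately. SAP 5.1 already plans a listing of each AE by subject, so a flag in that listing would do. Rows for the whole of follow-up should carry only the event classes that the reconciled rule collects throughout.

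**Cost.** A wording correction, one filter, and a short rule in the SAP for assigning coded events to head and neck or respiratory. The downside is that the labelled rates exclude unrelated non-serious systemic events, which appear only in the separate listing. The filter also cannot recover an in-scope event that a site never entered.
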